2.1.1 General definitions

Study treatment: IV Cipargamin and IV artesunate are randomized treatments. Coartem tablets (20/120 mg and 80/480 mg tablets) are used for oral therapy following the IV therapy for all patients. Coartem is not an investigational treatment and will not be presented in the treatment group name. Treatment group name will be used in statistical analyses and outputs. These treatment groups will be used as the column headers in the CSR outputs.

For example, the initial treatment groups in Cohort 1-2 will be displayed as:

- IV Cipargamin 20mg

- IV Cipargamin 40mg
- IV Artesunate

As per study design, other IV cipargamin dose levels may also be used. Treatment groups for each of the combinations will be used accordingly. For Cohorts 3 to 5, the IV Cipargamin dose level will be the equivalent dose level intended for patients ≥ 35 kg.

Baseline: The last measurement made prior to administration of the first dose of study treatment. Note: this may include measurements taken on the day of randomization (e.g. lab, ECG, vitals).

Study day: Study day will be calculated with respect to the first dose of study treatment. If a patient did not receive any dose of study treatment then the randomization date will be used as the date of first dose of study treatment. The first day of administration of study treatment (first dose) is defined as Day 1. Day -1 will be the day before Day 1. Day 0 does not exist. For some variables, assessments are collected more than once a day during first 3 days. Study day calculation for such assessments is based on the treatment start date and time.

For the assessments that are performed more than once a day: Study day = Integer (datetime of assessment – datetime of first dose of study treatment)/(60*60*24) + 1.

For assessments that are performed once for a day: Study day = date of assessment – date of first dose of study treatment + 1.

For assessments collected prior to Day 1, study day = date of assessment - date of first dose of study treatment.

Body temperature: Body temperature is measured using different routes (oral/rectal/tympanic/axillary), which will lead to variations in the readings. Therefore, all the temperature readings will be standardized with respect to tympanic equivalent as follows for the reporting purpose:

Body temperature (oral/tympanic/rectal equivalent) = Axillary temperature + 0.5°C.

Fever Clearance time (FCT) (in patients with temperature of $\geq 37.5^{\circ}\text{C}$ axillary or $\geq 38.0^{\circ}\text{C}$ oral/tympanic/rectal) is defined as time from the first IV study medication until the first time the body temperature decreased below and remained below 37.5°C axillary or 38.0°C oral/tympanic/rectal for at least a further 24 hours,

Parasite clearance time (PCT) is defined as time from the first IV study medication until the first total and continued disappearance of asexual parasite forms which remained at least a further 48 hours.

Parasitaemia: P. falciparum asexual parasite counts are based on the local lab assessment for all cohorts and repeated using central lab assessments for Cohorts 1 and 2. Similar use of local lab readings and central lab readings will be applied to PRR, recrudescence, reinfection, and clinical success below.

Parasite detection limit for central lab: 0.1 parasite/uL will be used as detection limit or assay sensitivity limit for the parasite counts using the central lab.

Parasite detection limit for local lab: 10 parasite/uL will be used as detection limit or assay sensitivity limit for the parasite counts using the central lab.

PRR is defined as the ratio of asexual parasite at baseline divided by asexual parasite at post-baseline. If the asexual parasite count at post-baseline is 0, the detection limit will be used to calculate the ratio.

Recrudescence and reinfection

Recrudescence is defined as appearance of asexual parasites after clearance of initial infection with a genotype identical to that of parasites present at baseline. Recrudescence must be confirmed by PCR analysis.

Reinfection or new infection is defined as appearance of asexual parasites after clearance of initial infection with a genotype different from those parasites present at baseline.

Clinical success

Clinical success is a composite endpoint defined based on the following criteria.

A patient is said to have achieved the clinical success at a given timepoint if the patient did not die either during the initial hospitalization nor due to malaria post the initial hospitalization, shows absence of *P. falciparum* asexual parasites, and did not have any of the key signs or symptoms of severe malaria on that given timepoint.

Note: Deaths occurring post initial hospitalization will be evaluated by designated adjudication committee to confirm if they are related to malaria.

Key signs of Severe Malaria

Key signs of Severe Malaria are Altered consciousness, Renal impairment, Acidosis, and Respiratory distress.

Signs of severe malaria

The following signs of severe malaria will be monitored at every visit during the entire study duration.

- **Altered consciousness** – Prostration (inability to sit or drink or breast feed) or GCS < 11 for patients > 5 years / BCS < 3 for patients ≤ 5 years of age
- **Renal Impairment** - Serum creatinine > 3xULN or > 3 mg/dL or need for renal replacement therapy (RRT)
- **Acidosis** - Plasma lactate > 4 mmol/L or Respiratory distress.
Respiratory distress is defined as rapid, deep and labored breathing (costal indrawing, use of accessory muscles and nasal flaring)- present or absent.
In database, Plasma lactate is captured under lactic acid.
- **Severe anemia** - Hb < 5 g/dl or Hb < 7g/dl in pediatric and adults respectively or need of blood transfusion
- **Jaundice** - Serum bilirubin > 3 mg/dl
- **Hypoglycemia**- plasma glucose < 40 mg/dL
- **Blantyre coma scale (BCS)** is a number from 0 to 5 based on [Appendix 5, Table 5-1](#) for patients ≤ 5 years. The score is determined by adding the results from three categories: Motor response, verbal response, and eye movement. The minimum score is 0 which indicates poor results while the maximum is 5 indicating good results.

- **Glasgow Coma Scale (GCS)** is a clinical scale used to reliably measure a person's level of consciousness for age > 5 years. The score is determined by adding the results from three categories: Motor response, verbal response, and eye movement. A person's GCS score can range from 3 (completely unresponsive) to 15 (responsive) based on [Appendix 5, Table 5-2](#).

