5.2.4 Visit windows

When visit windows are used, all visits will be re-aligned, i.e., they will be mapped into one of the visit windows. E.g., if the Day 4 visit of a patient is delayed and occurs on Day 7, say, it will be re-aligned to visit window Day 8. In the case of major deviations from the visit schedule, or due to unscheduled visits, several assessments of a patient may fall in a particular visit window (either scheduled or unscheduled). Statistical approaches to handle multiple assessments in a given visit window are specified below.

- Of note, patients are allowed to have gaps in visits. All data collected will be displayed in listings.
- The following rules are used to determine the window for other visits post baseline:
 - “Lower limit” = “upper limit of prior applicable visit” + 1.
 - “Upper limit” = “target day of current visit” + integer part of (“target day of next applicable visit” – “target day of current visit”)/2
 - No upper limit for Day 29 visit to include all assessments

For assessments that are scheduled to be performed only once on a day, [Table 5-8](#) describes the analysis windows mapping to visits (not just scheduled visits) based on study days alone. For the assessments that may be performed on multiple timepoints on a day, [Table 5-9](#) describes the analysis windows mapping to visits based on study day and time. Repeat and/or unscheduled visits (which will be numbered in the database according to new NCDS standards) will be mapped for analysis purposes in the same way. If there are multiple measurements within an analysis window, the conventions defined in [Table 5-10](#) will be used to determine the appropriate measurement to be selected for analysis.

The mapped visits will be used in the by visit analyses. However, the listings will show all collected data regardless of used in the by visit analyses.

Table 5-8 Analysis visit windows based on study days alone

Analysis Visit	Target Day	Analysis visit window for assessment group					
		ECG	Body weight ¹	Body height/Head circumference/body weight ²	INR/LDH	AAG	
Baseline	1	Up to Day 1	Up to Day 1	Up to Day 1	Up to Day 1	Up to Day 1	
Day 2	2	Day 2	Day 2-15	NA	NA	Day 2	
Day 3	3	Day 3	NA	NA	NA	Day 3 and above	
Day 4	4	Day 4 to Day 16	NA	NA	NA	NA	
Day 6	6	NA	NA	NA	NA	NA	
Day 8	8	NA	NA	NA	Day 2 and above	NA	
Day 15	15	NA	NA	NA	NA	NA	
Day 22	22	NA	NA	NA	NA	NA	
Day 29/ End of study	29	Day 17 and above	Day 16 and above	Day 2 and above	NA	NA	

¹ Cohorts 1-3 ² Cohorts 4-5

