Table 5-9 Analysis visit windows based on study day and time

Target visit	Target timepoint	Blood smear	PK (Cohorts 1 to 3)	PK (Cohorts 4-5)	Neurological/severe malaria assessment/ body temperature/blood pressure/pulse	Blood chemistry/hematology Point of Care device	Urinalysis
Baseline	0 hrs	up to 0 hrs	up to 0 hrs	NA	up to 0 hrs	up to 0 hrs	up to 0 hrs
Day 1	2 m	NA	>0 – 6m	>0 – 31 min	NA	NA	NA
	10 m	NA	>6m – 35 m	NA	NA	NA	NA
	30 m	NA	NA	NA	>0 – 3.25 hrs ¹	NA	NA
	1 hrs	>0 - 1.5 hrs	>35 m- 2.5 hrs	>31 min- 12.5 hrs	NA	NA	NA
	2 hrs	>1.5 – 3 hrs	NA	NA	NA	NA	NA
	4 hrs	>3 – 5 hrs	>2.5 – 8 hrs	NA	NA	NA	NA
	6 hrs	>5 - 9 hrs	NA	NA	>3.25-9 hrs	> 0 – 9 hrs ²	NA
	12 hrs	>9 - 15 hrs	>8- 18 hrs	NA	>9 - 15 hrs	>9 – 18 hrs	NA
	18 hrs	>15 - 21 hrs	NA	NA	>15 - 21 hrs	NA	NA
Day 2	24 hrs	>21 – 27 hrs	>18 – 24 hrs 1 min	>12.5 hrs – 36 hrs	>21 – 30 hrs	>18 -30 hrs	>0 – 30 hrs
	24 hrs 2 min	NA	>24 hrs 1 min-24 hrs 31 min	NA	NA	NA	NA
	25 hrs	NA	>24 hrs 31 min– 30.5 hrs	NA	NA	NA	NA
	30 hrs	>27 – 33 hrs	NA	NA	NA	NA	NA
	36 hrs	>33 – 39 hrs	>30.5 –42 hrs	NA	>30 – 42 hrs	>30 – 42 hrs	>30 -42 hrs

Target visit	Target timepoint	Blood smear	PK (Cohorts 1 to 3)	PK (Cohorts 4-5)	Neurological/severe malaria assessment/ body temperature/blood pressure/pulse	Blood chemistry/hematology Point of Care device	Urinalysis
	42 hrs	>39- 45 hrs	NA	NA	NA	NA	NA
Day 3 e	48 hrs	>45 – 60 hrs	m>42 – 48 hrs 1 min	>36 hrs	>42 -60 hrs	>42 -60 hrs	>42 – 60 hrs
	48 hrs 2 min	NA	>48 hrs 1 min – 48 hrs 31 min	NA	NA	NA	NA
	49 hrs	NA	>48 hrs 31 min – 54.5 hrs	NA	NA	NA	NA
	60 hrs	NA	>54.5 – 66 hrs	NA	NA	NA	NA
Day 4	72 hrs	>60 hrs to Day 5	>66 – 96 hrs	NA	>60 hrs to Day 5	>60 hrs to Day 5	>60 hrs to Day 5
Day 6	120 hrs	Day 6 – 7	>96 hrs – 144 hrs	NA	Day 6 – 7	Day 6 – 7	Day 6 -7
Day 8	168 hrs	Day 8 - 11	>144 hrs	NA	Day 8 - 11	Day 8 – 11	Day 8 -11
Day 15	336 hrs	Day 12 - 18	NA	NA	Day 12 - 18	Day 12 – 18	Day 12 - 18
Day 22	504 hrs	Day 19 - 25	NA	NA	Day 19 - 25	Day 19 - 25	Day 19 - 25
Day 29	672 hrs	Day 26 and above	NA	NA	Day 26 and above	Day 26 and above	Day 26 and above

¹ for body temperature and vital signs; ² for Point of Care device

Table 5-10 Rules for flagging variables

Timing of measurement	Type of data	Rule
Baseline	All data	The last measurement made prior to administration of the first dose of study treatment – note this may include measurements taken on the day of randomization. If a patient did not receive any dose of study treatment then the randomization date will be used.

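### The SAP's elapsed-time study day makes the non-PK Day 6 and Day 8 windows open exactly at target, so a visit held earlier in the clock day than the first dose falls in the previous window; the SAP should say which study-day formula applies after 72 h

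*SAP*

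**What the plan says.** SAP 2.1.1 has two post-dose formulas for study day. The first is introduced by variable: "For some variables, assessments are collected more than once a day during first 3 days. Study day calculation for such assessments is based on the" date and time of treatment start. It reads "Study day = Integer (datetime of assessment – datetime of first dose of study treatment)/(60*60*24) + 1". The second is "For assessments that are performed once for a day: Study day = date of assessment – date of first dose of study treatment + 1".

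SAP 5.2.4 sends assessments that may be made at several timepoints in a day to Table 5-9, whose windows rest on study day and time. For blood smear, neurological and severe-malaria signs, temperature, blood pressure and pulse, point-of-care chemistry and haematology, and urinalysis, that table uses hours up to 60 h and whole days afterwards. The 72 h visit takes ">60 hrs to Day 5", the Day 6 visit takes Days 6 to 7, and the Day 8 visit takes Days 8 to 11. The PK column for Cohorts 1 to 3 stays in hours, with ">96 hrs – 144 hrs" for Day 6 and everything after 144 h for Day 8.

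Table 5-10 keeps, for parasite counts, temperature and visit summaries, the value nearest the target. The example in 5.2.4 says that a delayed Day 4 visit that "occurs on Day 7, say, it will be re-aligned to visit window Day 8".

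The protocol's assessment schedules (Tables 8-1 and 8-2) set Days 6 and 8 at 120 h and 168 h without a tolerance, and Days 15, 22 and 29 with tolerances of 1, 2 and 2 days.

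**The concern.** Under the elapsed-time formula the day number changes at the clock time of the first dose, not at midnight. Whole-day windows built for calendar days then leave no room before target at Days 6 and 8. First doses follow emergency admission and can fall at any hour, while follow-up visits may be held at a different time of day. A participant who attends on the correct date can therefore have the record dropped from a table or shown under the wrong visit.

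At stake are clinical success at Days 6 and 8, the shift tables of severe-malaria signs, and the vital-sign and laboratory tables at those visits. Two programmers reading the SAP in good faith could produce different tables. The Day 7 example conflicts with Table 5-9 on either reading.

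**Working it through.** **Inputs.** Study-day formulas from SAP 2.1.1; window rule and Table 5-9 from SAP 5.2.4; selection rule from Table 5-10; target hours from protocol Tables 8-1 and 8-2. I read the integer function as applying to the whole quotient. As printed it encloses only the difference in seconds, which would give fractional days.

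**Reproducing the plan's windows.** By the 5.2.4 rule, upper limit = target day + integer part of (next target − target)/2, and each lower limit is the previous upper limit plus 1.

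- Day 4: 4 + INT(2/2) = 5
- Day 6: 6 + INT(2/2) = 7, window 6 to 7
- Day 8: 8 + INT(7/2) = 11, window 8 to 11
- Day 15: 15 + INT(7/2) = 18, window 12 to 18
- Day 22: 22 + INT(7/2) = 25, window 19 to 25
- Day 29: 26 and above

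These match Table 5-9, so its limits are sound as integer-day limits.

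**Where the windows open in elapsed time.** INT(120/24) + 1 = 6 and INT(168/24) + 1 = 8. Study Day 6 begins at 120 h and study Day 8 at 168 h, exactly on target.

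**Worked case: first dose 16:00, visits at 10:00 on the correct dates.**

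- Day 6 visit: 5 × 24 − 6 = 114 h; INT(114/24) + 1 = 5, so it falls in the 72 h window. The 72 h record is 0 h from target and this one is 114 − 72 = 42 h away, so it is not selected.
- Day 8 visit: 7 × 24 − 6 = 162 h; INT(162/24) + 1 = 7, so it is labelled Day 6. Nothing remains for Day 8.

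**Other patterns.**

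| Records at (h) | 72 h visit | Day 6 | Day 8 | Not selected |
|---|---|---|---|---|
| 72, 118, 166 | 72 | 166 | empty | 118 |
| 72, 121, 166 | 72 | 121 | empty | 166 |
| 72, 118, 169 | 72 | empty | 169 | 118 |
| 118, 166 | 118 | 166 | empty | none |

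**The other two approaches in the SAP.** With the calendar formula, every visit on calendar Day 6 or Day 8 maps to its own window. With the PK column's hour windows, 118 h maps to Day 6 and 166 h to Day 8.

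**Later visits.** The Day 15, 22 and 29 windows open on study Days 12, 19 and 26, that is at 264, 432 and 600 h. The earliest visit within tolerance, with a clock shift just under 24 h, comes just after 336 − 24 − 24 = 288, 504 − 48 − 24 = 432 and 672 − 48 − 24 = 600 h. None is misassigned.

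**Share affected, by assumption only.** The share is the probability that the first-dose clock time is later than the visit clock time. With doses uniform over 24 h it is 14/24 = 58% for 10:00 visits and 10/24 = 42% for 14:00 visits. With doses uniform from 08:00 to 20:00 it is 10/12 = 83% and 6/12 = 50%.

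**The case against.** The SAP may already contain the remedy. Smears, signs and laboratory tests are done once on Day 6 and once on Day 8, so the formula for assessments performed once a day can be read as covering those visits. The layout of Table 5-9 supports this: the non-PK columns change from hours to whole days after 60 h, and their limits follow the calendar-type integer rule. On that reading nothing is misassigned. This stands as a possible reading. But SAP 2.1.1 attaches the elapsed-time formula to variables, Table 5-9 is said to rest on study day and time, and no sentence announces a switch at follow-up.

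Several objections to the size of the effect also stand:

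- The documents give no clock times for doses or visits, so the percentages above are illustrations.
- Collected data are not lost. The listings show everything, and notable abnormalities use the most extreme value in a window, so those are relabelled and not removed.
- A reader might infer that an attended Day 8 visit would be scored under the skipped-visit rule of Table 2-4, taking the worse of its neighbours. The SAP does not apply that rule to an attended visit that was re-windowed.
- SAP 2.7.1 lists Day 6 clinical success, but the analysis text in 2.7.2.1 and Table 2-4 omit Day 6.
- A reader might also expect trouble from LDH and haemoglobin being dated differently. Table 5-8 maps any LDH from Day 2 onwards to Day 8, and delayed haemolysis uses the closest value if Day 8 is missing, so little follows.
- The difference in labels between PK and smear concerns Cohorts 1 to 3 only, since Cohorts 4 and 5 have no Day 6 or Day 8 PK sample.

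**Conclusion.** The point holds as a gap in specification with a definite consequence on the natural reading. If the elapsed-time formula is used throughout for the Table 5-9 variables, any non-PK assessment made on calendar Day 6 or Day 8 at an earlier clock time than the first dose lands in the previous window. The Day 6 record then usually loses to the 72 h record, the Day 8 record is labelled Day 6 or dropped, and Day 8 may be empty.

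The effect is confined to Day 6 and Day 8 by-visit summaries. The 12 h primary endpoint, the 48 h key secondary endpoint, PK, the time-to-event analyses (which run from first dose to event) and Days 15 to 29 are not affected. The documents do not support the inference that most participants would be misassigned, because that rests on assumed clock times. Nor do they show any imbalance between arms.

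The Day 7 example is wrong for the non-PK columns on either reading: Table 5-9 and the upper-limit rule both put Day 7 in the Day 6 window.

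**What to change.** State in SAP 2.1.1 and beside Table 5-9 that the calendar-date study-day formula applies to all non-PK assessments after 72 h.

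Alternatively, where clock times are recorded at follow-up, replace the whole-day limits by hour windows cut at the midpoints between targets: >60 to 96 h (72 h visit), >96 to 144 h (Day 6), >144 to 252 h (Day 8), >252 to 420 h (Day 15), >420 to 588 h (Day 22) and >588 h (Day 29). The cut-offs are (72 + 120)/2 = 96, (120 + 168)/2 = 144, (168 + 336)/2 = 252, (336 + 504)/2 = 420 and (504 + 672)/2 = 588. The protocol asks for exact times of follow-up PK samples but has no matching instruction that I could find for follow-up smears, signs or laboratory tests, so the calendar formula is the safer choice.

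In either case, correct the example in SAP 5.2.4 so that a Day 7 assessment maps as in Table 5-9, and place the integer function around the whole quotient in 2.1.1.

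The cost is SAP wording and one derivation, settled before database lock. The calendar version needs no new data.

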2.2 Analysis sets

Randomized set

All patients who are randomized into the study.

Full analysis set (FAS)

FAS will be comprised of all patients from Randomized set who take at least one dose of study treatment during the treatment period and whose baseline *P. Falciparum* asexual parasitaemia count is greater than 0 using local lab (central lab in case local lab assessment is not available). Following the intent-to-treat principle, patients will be analyzed according to the treatment group assigned to at randomization.

Unless otherwise specified, misrandomized patients will be excluded.

Misrandomized patients, if identified from IRT, include screen-failures, but have been randomized by the investigator before eligibility was finally assessed or mistakenly, and have not been treated. If patients were re-screened and successfully randomized, they will be included according to the treatment assigned in the last randomization.

Safety set (SAF)

Safety set includes all patients who take at least one dose of study drug during the treatment period. Patients will be analyzed according to treatment received. In particular, patient will be analyzed in the same treatment group as randomized if s/he receives at least one dose of the study medication of that group.

Per-protocol set (PPS)

Per-protocol set will be comprised of patients in FAS who did not have any important protocol deviations affecting efficacy.

Important protocol deviations and non-protocol deviations for exclusion from PPS are specified in [Table 5-15](#) and will be identified by the clinical team before the database lock.

PK analysis set

All patients who have at least one valid (i.e. not flagged for exclusion) PK concentration measurement, receive at least one dose of study drug, and do not have any protocol deviations that have an impact on PK data.

2.2.1 Subgroup of interest

The following subgroups will be used for descriptive summary of the selected efficacy and safety analyses in all cohorts pooled. The details will be provided in the corresponding sections.

- Age groups as per [Section 2.3](#)
- Baseline weight groups as per [Section 2.3](#)
- Sex (male vs female)
- Different level of baseline HRP2 as per [Section 2.3](#)
- Geographic region (Africa, Asia)
- Use of previous antimalarial therapy before screening (Yes/No, stratification factor)

In addition, if deemed appropriate, additional subgroup analysis may be performed for data exploration; such as different *P. falciparum* gene resistance markers.

2.3 Patient disposition, demographics and other baseline characteristics

2.3.1 Medical history

Any condition entered on the *Relevant medical history / current medical conditions* CRF will be coded using the MedDRA dictionary. They will be summarized by system organ class (SOC), preferred term (PT) and treatment group for each cohort, for Cohorts 1 and 2 pooled and all cohorts pooled. A summary will also be provided of medical conditions that were ongoing at the time of screening.

Clinically relevant findings that are present prior to signing informed consent must be recorded on the appropriate CRF that captures medical history. Significant findings made after signing informed consent which meet the definition of an Adverse Event must be recorded as an adverse event. The findings occurring after signing ICF and before start of the study treatment will be listed.

Analyses will be based on the Full analysis set.

2.3.2 Patient demographics and other baseline characteristics

Demographic data and baseline disease characteristics will be descriptively presented and tabulated per treatment group, as well as overall, using FAS and PPS. If there are patients in the SAF excluded from FAS, a summary will also be provided for the SAF.

The following demographic variables will be summarized:

- Age and age categories (6 m to < 2 yrs, 2 to <6 yrs, 6 to <12 yrs, 12 to <18 yrs, 18 to <65 yrs, and ≥ 65 , <18 vs ≥ 18 yrs)
- Sex (male, female)
- Race (Caucasian, black, Asian, native American, pacific islander, unknown, other)

- Ethnicity
- Body weight and weight categories (5 to <10, 10 to <15, 15 to <25, 25 to <35, 35 to <55, and ≥ 55 kg)
- Body height (cm)
- BMI and BMI categories (<16, 16 to 25, >25) (Kg/m^2)
- Head circumference <cm>(for Cohort 5)

The following disease characteristics at baseline will be summarized

- Body temperature and categories equivalent to tympanic method (<38, 38 to <39, ≥ 39) ($^{\circ}\text{C}$)
 - *Falciparum* species: (*P. Falciparum* asexual forms, *P. Falciparum* gametocytes, *P. Vivax*, *P. Ovale*, *P. malariae*, *P. Knowlesi*, and Mixed-infection (two or more of *Falciparum* asexual forms, *P. Vivax*, *P. Ovale*, *P. malariae*, *P. Knowlesi*), n (%)) using local lab for all patients as well as central lab for patients in Cohorts 1 and 2.
- *P. falciparum* density per micro ltr. and its categories (5,000 to <15,000, 15,000 to <50,000, 50,000 to <100,000, 100,000 to <150,000, 150,000 to < 200,000, $\geq 200,000$ parasites/ μL ; <100,000 / μL , $\geq 100,000$ parasites / μL) using local lab for all patients as well as central lab for patients in Cohorts 1 and 2.
- Gametocytes counts / μL
- Results of gene resistance markers of *P. falciparum*
- Baseline HRP2 concentrations ng/ml
- Baseline HRP2 concentration categories ng/ml (≤ 33 th percentile, 34th to 67th percentile, >67 th percentile; < median, \geq median)
- Results of AAG
- HRP2/platelet status: plasma HRP2 >1000 ng/ml and <200,000 platelets/microliter

Note- Categories that are with non-zero counts will be displayed.

